5.3. Lifestyle Considerations

The following guidelines are provided:

5.3.1. Meals and Dietary Restrictions

- Participants must abstain from all food and drink (except water) at least 4 hours prior to any safety laboratory evaluations (includes hematology, chemistry, urinalysis and coagulation test).
- At least a 2-hour fast is required before and after drug administration for all dose.
- Water is restricted 1 hour prior to study intervention administration for all doses (except water used to swallow drugs). Water may be consumed without restriction beginning 1 hour after morning dosing of Day 1 and Day 10, and may be consumed without restriction after morning dosing on non-PK days and all evening doses. Noncaffeinated drinks (except grapefruit or grapefruit-related citrus fruit juices—see below) may be permitted with meals and the evening snack.
- An evening snack may be permitted.
- Participants will refrain from consuming red wine, grapefruit, or grapefruit-related citrus fruits (eg, Seville oranges, pomelos, fruit juices) from 7 days prior to the first dose of study intervention until collection of the final PK blood sample.
- While participants are confined, all meals need to provided by clinical research unit as standard meal.

5.3.2. Caffeine, Alcohol, and Tobacco

- Participants will abstain from caffeine-containing products for 24 hours prior to the start of dosing until collection of the final PK sample.
- Participants will abstain from alcohol for 24 hours to admission to the CRU and continue abstaining from alcohol until collection of the final PK sample. Participants may undergo an alcohol breath test or blood alcohol test at the discretion of the investigator.
- Participants will abstain from the use of tobacco- or nicotine-containing products for 24 hours prior to dosing and during confinement in the CRU.

5.3.3. Activity

- Participants will abstain from strenuous exercise (eg, heavy lifting, weight training, calisthenics, aerobics) for at least 48 hours prior to each blood collection for clinical laboratory tests. Walking at a normal pace will be permitted;

- In order to standardize the conditions on PK sampling days, participants will be required to maintain daily activities (such as sitting or walking at a normal pace, except when required for BP, PR, and ECG measurements), and refrain from drinking beverages other than water during the first 2 hours after dosing.

5.3.4. Contraception

The investigator or his or her designee, in consultation with the participant, will confirm that the participant has selected an appropriate method of contraception for the individual participant from the permitted list of contraception methods (see [Appendix 4 Section 10.4.4](#)) and will confirm that the participant has been instructed in its consistent and correct use. At time points indicated in the schedule of activities ([SoA](#)), the investigator or designee will inform the participant of the need to use highly effective contraception consistently and correctly and document the conversation and the participant's affirmation in the participant's chart (participants need to affirm their consistent and correct use of at least 1 of the selected methods of contraception) considering that their risk for pregnancy may have changed since the last visit. In addition, the investigator or designee will instruct the participant to call immediately if the selected contraception method is discontinued or if pregnancy is known or suspected in the participant or partner.

5.4. Screen Failures

Screen failures are defined as participants who consent to participate in the clinical study but are not subsequently enrolled in the study. Screen failure data are collected and remain as source and are not reported on the CRF.

Individuals who do not meet the criteria for participation in this study (screen failure) may be rescreened, at the discretion of the investigator.

6. STUDY INTERVENTION(S) AND CONCOMITANT THERAPY

Study intervention is defined as any investigational intervention(s), marketed product(s), placebo, medical device(s), or study procedure(s) intended to be administered to a study participant according to the study protocol.

For the purposes of this protocol, study intervention refers to PF-07321332 and ritonavir.

6.1. Study Intervention(s) Administered

PF-07321332 will be provided by Pfizer as tablet at the CRU, and will be supplied to the CRU in bulk bottle and will dispensed in individual dosing containers for unit dosing to participants.

Ritonavir will be provided by Pfizer as 100 mg tablets.

6.1.1. Administration

Investigational products will be administered orally and according to the conditions described in the [SoA](#) section and Protocol [Section 5.3.1 Meals and Dietary Restrictions](#).

On Day 1 following a fast of at least 2 hours, participants will receive 300 mg PF-07321332, administered orally with 100 mg ritonavir (as 1 × 100 mg tablet) administered orally starting in the morning. PF-07321332 and ritonavir will be dosed simultaneously (within no more than 5 minutes of each other). Participants will receive 300 mg PF-07321332, with 100 mg ritonavir (as 1 × 100 mg tablet) administered orally q12h (±30 min) for a total of 19 doses, with the last dose administered on the morning of Day 10 (no evening dose on Day 10). The dose interval between first dose and second dose on Day 1 needs to be no less than 12 hours, to allow 12 hours for sample collection prior to start of Day 1 evening dosing. Participants will swallow both tablets whole and will not chew prior to swallowing.

Investigator site personnel will administer study intervention with ambient temperature water to a total volume of approximately 240 mL. Study intervention will be administered according to the protocol.

6.2. Preparation, Handling, Storage, and Accountability

1. The investigator or designee must confirm appropriate temperature conditions have been maintained during transit for all study interventions received and any discrepancies are reported and resolved before use of the study intervention.
2. Only participants enrolled in the study may receive study intervention and only authorized site staff may supply or administer study intervention. All study interventions must be stored in a secure, environmentally controlled, and monitored (manual or automated recording) area in accordance with the labeled storage conditions with access limited to the investigator and authorized site staff. At a minimum, daily minimum and maximum temperatures for all site storage locations must be documented and available upon request. Data for nonworking days must indicate the minimum and maximum temperatures since previously documented for all site storage locations upon return to business.
3. Any excursions from the study intervention label storage conditions should be reported to Pfizer upon discovery along with any actions taken. The site should actively pursue options for returning the study intervention to the storage conditions described in the labeling, as soon as possible. Once an excursion is identified, the study intervention must be quarantined and not used until Pfizer provides permission to use the study intervention. Specific details regarding the definition of an excursion and information the site should report for each excursion will be provided to the site in the IP manual or other specified location.
4. Any storage conditions stated in the SRSD will be superseded by the storage conditions stated on the label.
5. Study interventions should be stored in their original containers.
6. The investigator, institution, or the head of the medical institution (where applicable) is responsible for study intervention accountability, reconciliation, and record

maintenance (ie, receipt, reconciliation, and final disposition records), such as the IPAL or sponsor-approved equivalent. All study interventions will be accounted for using a study intervention accountability form/record.

7. Further guidance and information for the final disposition of unused study interventions are provided in the IP manual or other specified location. All destruction must be adequately documented. If destruction is authorized to take place at the investigator site, the investigator must ensure that the materials are destroyed in compliance with applicable environmental regulations, institutional policy, and any special instructions provided by Pfizer.

Upon identification of a product complaint, notify the sponsor within 1 business day of discovery as described in the IP manual.

6.2.1. Preparation and Dispensing

Within this protocol, preparation refers to the investigator site activities performed to make the study intervention ready for administration or dispensing to the participant by qualified staff. Dispensing is defined as the provision of study intervention, concomitant treatments, and accompanying information by qualified staff member(s) to a healthcare provider, participant in accordance with this protocol. Local health authority regulations or investigator site guidelines may use alternative terms for these activities.

See the package insert, or equivalent for instructions on how to prepare the study intervention (ritonavir) for administration. Study intervention should be prepared and dispensed by an appropriately qualified and experienced member of the study staff (eg, physician, nurse, physician's assistant, nurse practitioner, pharmacy assistant/technician, or pharmacist) as allowed by local, state, and institutional guidance. A second staff member will verify the dispensing.

Tablets (PF-07321332) will be prepared at the CRU as single dose and provided to participants by 2 operators, 1 of whom is an appropriately qualified and experienced member of the study staff (eg, physician, nurse, physician's assistant, nurse practitioner, pharmacy assistant/technician, or pharmacist). The tablets will be provided in unit dose containers and labeled in accordance with Pfizer regulations and the clinical site's labeling requirements.

6.3. Measures to Minimize Bias: Randomization and Blinding

6.3.1. Allocation to Study Intervention

The investigator's knowledge of the treatment should not influence the decision to enroll a particular participant or affect the order in which participants are enrolled.

The investigator will assign participant numbers to the participants as they are screened for the study. Pfizer will provide a randomization schedule to the investigator and, in accordance with the randomization numbers, the participant will receive the study treatment regimen assigned to the corresponding randomization number.

6.4. Study Intervention Compliance

When the individual dose for a participant is prepared from a bulk supply, the preparation of the dose will be confirmed by a second qualified member of the study site staff.

When participants are dosed at the site, they will receive study intervention directly from the investigator or designee, under medical supervision. The date and time of each dose administered in the clinic will be recorded in the source documents and recorded in the CRF. The dose of study intervention and study participant identification will be confirmed at the time of dosing by a member of the study site staff other than the person administering the study intervention. Study site personnel will examine each participant's mouth to ensure that the study intervention was ingested.

6.5. Dose Modification

No dose modification is anticipated.

6.6. Continued Access to Study Intervention After the End of the Study

No intervention will be provided to study participants at the end of their study participation.

6.7. Treatment of Overdose

For this study, any dose of PF-07321332 greater than 600 mg or ritonavir greater than 200 mg within a 24-hour time period ± 2 hours will be considered an overdose.

There is no specific treatment for an overdose.

In the event of an overdose, the investigator should:

1. Contact the medical monitor within 24 hours.
2. Closely monitor the participant for any AEs/SAEs and laboratory abnormalities for at least 5 half-lives or 28 calendar days after the overdose of PF-07321332 or ritonavir (whichever is longer).
3. Document the quantity of the excess dose as well as the duration of the overdose in the CRF.
4. Overdose is reportable to Pfizer Safety **only when associated with an SAE**.
5. Obtain a blood sample for PK analysis within 1 days from the date of the last dose of study intervention if requested by the medical monitor (determined on a case-by-case basis).

Decisions regarding dose interruptions or modifications will be made by the investigator in consultation with the medical monitor based on the clinical evaluation of the participant.

6.8. Concomitant Therapy

Use of prescription or nonprescription drugs and dietary and herbal supplements are prohibited within 7 days or 5 half-lives (whichever is longer) prior to the first dose of study intervention. Limited use of nonprescription medications that are not believed to affect participant safety or the overall results of the study may be permitted on a case-by-case basis following approval by the sponsor. Acetaminophen/paracetamol may be used at doses of ≤ 1 g/day.

Hormonal contraceptives that meet the requirements of this study are allowed to be used in participants who are WOCBP (see [Appendix 4](#)).

Females using hormonal contraceptives or taking hormone replacement therapy may be eligible to participate in this study if they are willing to discontinue therapy at least 28 days prior to the first dose of study treatment and remain off hormonal therapy for the duration of the study. Depo-Provera® must be discontinued at least 6 months prior to the first dose of study treatment.

All concomitant treatments taken during the study must be recorded with indication, daily dose, and start and stop dates of administration. All participants will be questioned about concomitant treatment at admission.

Treatments taken within 28 days before the first dose of study intervention will be documented as a prior treatment. Treatments taken after the first dose of study intervention will be documented as concomitant treatments.

6.8.1. Rescue Medicine

There is no rescue therapy to reverse the AEs observed with PF-07321332 and ritonavir; standard medical supportive care must be provided to manage the AEs, at the discretion of investigators.

7. DISCONTINUATION OF STUDY INTERVENTION AND PARTICIPANT DISCONTINUATION/WITHDRAWAL

7.1. Discontinuation of Study Intervention

It may be necessary for a participant to permanently discontinue study intervention. Reasons for permanent discontinuation of study intervention include the following:

- AE requiring discontinuation in investigator's view;
- Pregnancy;
- Positive COVID-19 test.

If study intervention is permanently discontinued, the participant will not remain in the study for further evaluation. See the [SoA](#) for data to be collected at the time of discontinuation of study intervention.

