1.3. Schedule of Activities

The SoA table provides an overview of the protocol visits and procedures. Refer to the **STUDY ASSESSMENTS AND PROCEDURES** section of the protocol for detailed information on each procedure and assessment required for compliance with the protocol.

The investigator may schedule visits (unplanned visits) in addition to those listed in the SoA table, in order to conduct evaluations or assessments required to protect the well-being of the participant.

Visit Identifier ^a Abbreviations used in this table may be found in Appendix 7 .	Screening	Treatment												Follow-Up	Early Termination/ Discontinuation	
Days Relative to Day 1	Day -28 to Day -2	Day -1	Day 1	Day 2	Day 3	Day 4	Day 5	Day 6	Day 7	Day 8	Day 9	Day 10	Day 11	Day 12	28-35 Days ^b	
Informed consent	X															
CRU confinement ^c		X	→	→	→	→	→	→	→	→	→	→	→	→		
Inclusion/exclusion criteria	X	X														
Medical/medication history (update) ^d	X	X														
Physical exam (including height, body weight and BMI at Screening only) ^e	X	X											X		X	
Safety laboratory ^f	X	X	X			X				X		X		X		
TSH and free T4 ^g	X	X									X				X	
Thyroid ultrasound and antibody (aTPO, ATG) tests ^g	X	X														
Demography	X															
Pregnancy test (WOCBP only)	X	X										X			X	
Contraception check (Inquiry) ^h	X	X										X	X		X	
FSH ⁱ	X															
Urine drug testing ^j	X	X														
12-Lead ECG (triplicate) ^k	X		X								X				X	
Vital signs (BP/PR/RR/temperature) ^k	X		X								X				X	
Serology: HIV, HBsAg, HCVAb, HbCAb	X															
COVID-19 questionnaire ^l	X	X														
COVID-19 testing ^m	X ⁿ	X ⁿ														
COVID-19 check temperature ^o	X	X	X	X	X	X	X	X	X	X	X	X	X		X	
Study intervention administration ^p			X	X	X	X	X	X	X	X	X	X				
PK blood sampling ^q			X				X			X		X	X		X	
CCI																

PFIZER CONFIDENTIAL

Visit Identifier ^a Abbreviations used in this table may be found in Appendix 7 .	Screening	Treatment												Follow-Up	Early Termination/Discontinuation	
		Day -28 to Day -2	Day -1	Day 1	Day 2	Day 3	Day 4	Day 5	Day 6	Day 7	Day 8	Day 9	Day 10	Day 11	Day 12	28-35 Days ^b
CRU discharge ^c															X	
Serious and nonserious AE monitoring and follow-up	X	→	→	→	→	→	→	→	→	→	→	→	→	→	→	X

- a. Day relative to start of study intervention (Day 1).
- b. Contact may occur via telephone contact and must occur 28 to 35 days from administration of the final dose of study intervention.

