7.2. Participant Discontinuation/Withdrawal From the Study

A participant may withdraw from the study at any time at his/her own request. Reasons for discontinuation from the study include the following:

- Refused further study procedures;
- Lost to follow-up;
- Death;
- Study terminated by sponsor;
- Investigator's decision
- Pregnancy
- Other reasons that may make the participant not evaluable for the primary endpoints at the evaluation by investigators and sponsor.

At the time of discontinuing from the study, if possible, an early discontinuation visit should be conducted. See the [SoA](#) for assessments to be collected at the time of study discontinuation and follow-up and for any further evaluations that need to be completed.

If a participant withdraws from the study, he/she may request destruction of any remaining samples taken and not tested, and the investigator must document any such requests in the site study records and notify the sponsor accordingly.

If the participant withdraws from the study and also withdraws consent (see Section 7.2.1) for disclosure of future information, no further evaluations should be performed and no additional data should be collected. The sponsor may retain and continue to use any data collected before such withdrawal of consent.

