8.3.1. Time Period and Frequency for Collecting AE and SAE Information

The time period for actively eliciting and collecting AEs and SAEs ("active collection period") for each participant begins from the time the participant provides informed consent, which is obtained before the participant's participation in the study (ie, before undergoing any study-related procedure and/or receiving study intervention), through and including a minimum of 28 calendar days, except as indicated below, after the last administration of the study intervention.

Follow-up by the investigator continues throughout and after the active collection period and until the AE or SAE or its sequelae resolve or stabilize at a level acceptable to the investigator.

For participants who are screen failures, the active collection period ends when screen failure status is determined.

If the participant withdraws from the study and also withdraws consent for the collection of future information, the active collection period ends when consent is withdrawn.

If a participant permanently discontinues or temporarily discontinues study intervention because of an AE or SAE, the AE or SAE must be recorded on the CRF and the SAE reported using the CT SAE Report Form.

Investigators are not obligated to actively seek information on AEs or SAEs after the participant has concluded study participation. However, if the investigator learns of any SAE, including a death, at any time after a participant has completed the study, and he/she considers the event to be reasonably related to the study intervention, the investigator must promptly report the SAE to Pfizer using the CT SAE Report Form.

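### Protocol 7.1 removes participants who permanently stop study drug from further evaluation, contradicting the 28-day adverse event collection and the 28-35-day contact required elsewhere

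*Protocol*

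**What the plan says.** Protocol Section 7.1 lists an AE, pregnancy and a positive COVID-19 test among the reasons for permanently stopping study drug. It then says: "If study intervention is permanently discontinued, the participant will not remain in the study for further evaluation". Its only further instruction on data is to consult the Schedule of Activities (SoA) for what is collected when the drug is stopped.

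Other parts of the protocol say:

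- **Section 8.3.1.** Active collection of AEs and serious AEs runs for each participant "through and including a minimum of 28 calendar days, except as indicated below, after the last administration of the study intervention". The early endings are screen failure, and withdrawal from the study combined with withdrawal of consent. On stopping drug for an AE, it says that for anyone who "permanently discontinues or temporarily discontinues study intervention because of an AE or SAE, the AE or SAE must be recorded on the CRF"; it does not shorten the collection period. It also says: "Investigators are not obligated to actively seek information on AEs or SAEs after the participant has concluded study participation".
- **SoA (Section 1.3), footnote b.** The follow-up contact may be by telephone and "must occur 28 to 35 days from administration of the final dose of study intervention".
- **Section 7.2.** For those leaving the study: "At the time of discontinuing from the study, if possible, an early discontinuation visit should be conducted". It refers the site to the SoA, naming "assessments to be collected at the time of study discontinuation and follow-up and for any further evaluations that need to be completed". Where consent for future information is also withdrawn, "no further evaluations should be performed and no additional data should be collected".
- **Section 7.2.1.** Participants who themselves ask to stop the drug stay in the study and must be followed.

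**The concern.** Section 7.1 and Section 8.3.1 give opposite instructions for the same person. A participant taken off drug for an AE is, under 7.1, no longer evaluated. Under 8.3.1 and footnote b, that participant is owed at least 28 days of active AE collection and a mandatory contact.

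The contrast with 7.2.1 makes the result odd. A participant who simply asks to stop must be followed. One stopped for an AE is not retained, nor, if 7.1 governs, is one withdrawn from drug under the QTcF criteria in 7.1.1. Read literally, the protocol gives less structured follow-up to the participants of greatest safety interest.

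Safety and tolerability is a secondary objective, studied in about 14 healthy volunteers who gain no clinical benefit. SAP Section 3.5.1 counts events from first dose until before the end of the study as treatment-emergent. Late events in early stoppers would therefore enter the analysis if collected, but a site following 7.1 has no reason to ask about them.

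**Working it through.** The plan states no figure on this point, and the study is descriptive, so the check is a comparison of text plus a day count.

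**Step 1. Does 8.3.1 exempt participants who stop the drug?** It names two early endings: screen failure, and study withdrawal with consent also withdrawn. Stopping drug for an AE is discussed in the same section and is not a third. So 8.3.1 applies in full to the participant whom 7.1 removes.

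**Step 2. Does footnote b exempt them?** No. It counts from the final dose, whichever day that falls on. One caution: the footnote belongs to the SoA's Follow-Up column, and early termination has a separate column, so 8.3.1 is the firmer anchor.

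**Step 3. Does 7.2 resolve it?** In part. It sends study discontinuers to the SoA for follow-up, and it bars further evaluation only where consent is also withdrawn. But it does not state the 28-day window, makes the early visit conditional on feasibility, and does not say that it overrides 7.1.

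**Step 4. Does 7.2.1 resolve it?** Only for participants who request to stop. It does not cover a stop imposed for an AE.

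**Step 5. Contacts at stake.** After discharge on Day 12 a completer has 1 scheduled contact. For each dosed early stopper:

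| Site follows | Contacts made | Contacts lost |
|---|---|---|
| 7.2, 8.3.1 and footnote b | 1 | 1 − 1 = 0 |
| 7.1 literally | 0 | 1 − 0 = 1 (1 of 1) |

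**Step 6. When the contact would fall.** Window = last-dose day + 28 to last-dose day + 35.

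| Last dose | Window |
|---|---|
| Day 1 | Day 29 to Day 36 |
| Day 9 | Day 37 to Day 44 |
| Day 10 (completer) | Day 38 to Day 45 |

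**Step 7. What is collected regardless.** Known AEs are followed to resolution or stabilization (8.3.1, 8.3.3). Clinically significant laboratory abnormalities are repeated until settled (8.2.4), and pregnancies are followed to outcome (8.3.5.1). Anyone who took a dose stays in the safety analysis set (9.2). What remains exposed is new events in early stoppers that active questioning at the final contact would have found.

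**The case against.** The best defence is that 8.3.1 governs AE collection and already gives the answer, with footnote b working unchanged for any last-dose day. On this view, further evaluation in 7.1 means scheduled on-study pharmacokinetic and safety assessments, not AE collection. Section 7.2 supports that reading, because it bars evaluations and data collection as two separate things and only where consent is withdrawn. Section 7.1.2 also asks for on-site re-evaluation in potential acute kidney injury, in the same passage that discontinues confirmed cases from the study, so leaving does not bar safety evaluation. Finally, the sentence in 8.3.1 releasing the investigator turns on concluded participation, which the protocol does not define. Stopping drug need not trigger it.

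Much of this stands. A careful site can reconcile the text, and nothing shows that the sponsor meant to drop follow-up. But the narrower reading of 7.1 is nowhere stated. The kidney injury provision concerns a finding already made, not the search for new events. A site that takes 7.1 to mean participation has ended can point to the release sentence in 8.3.1 as support for making no contact. The defence limits the consequence; it does not remove the contradictory sentence.

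**Conclusion.** The concern holds. Section 7.1 contains a stated rule that conflicts with 8.3.1, with footnote b and, for those who ask to stop, with 7.2.1; Section 7.2 only partly repairs it. The effect is 0 or 1 contact per dosed early stopper, depending on which section the site follows. The one at risk is the only scheduled contact after discharge.

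No expected number of missed contacts or events is claimed, because the documents give no discontinuation rate; the lower bound is zero. The upper figure assumes a site that applies 7.1 literally. The primary pharmacokinetic endpoints and the sample size are unaffected. This should be fixed because the affected participants include those stopped for AEs and the correction is small. Confidence in the textual conflict is high. Whether any event would actually be missed cannot be judged from the documents.

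**What to change.** Replace the quoted sentence in Section 7.1 with:

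> A dosed participant who permanently discontinues study intervention will receive no further doses, will complete the early-termination assessments where possible (Section 7.2), and will remain in safety follow-up, with AEs/SAEs collected per Section 8.3.1 through the 28-35-day contact in the SoA, unless consent for follow-up is withdrawn.

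The cost is one sentence in a protocol amendment. Under Section 10.1.1 that needs ethics committee approval, plus health authority approval if the amendment is classed as substantial. No visit or procedure is added: the early-termination assessments stay conditional on feasibility, as in 7.2, and the contact is already in the SoA and may be by telephone.
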